c) Mortality: Patients with moderate and advanced CKD appear to have a high risk of death with both high and low serum bicarbonate (U-shaped association). In a study of 1,250 CKD patients, the risk of death increased by 43% when bicarbonate level was  $<22$  mEq/L and by 24% with a bicarbonate level  $>29$  mEq/L.

9. Bicarbonate administration in CKD. Alkali therapy is currently recommended in CKD patients when the serum bicarbonate level is  $<22$  mEq/L to mitigate the effects of acidosis on bone and protein. However,  $>80\%$  of CKD patients have normal serum bicarbonate levels and do not receive alkali despite the fact that they are in positive acid balance. As discussed earlier, interventional studies have found that alkali slows CKD progression in people with normal serum bicarbonate levels. Even though no interventional trials have been performed examining the effect of alkali on CVD, results from observational studies support the hypothesis that alkali replacement may also reduce cardiovascular risk, even in patients with normal bicarbonate. Hence, a major paradigm shift in the treatment of CKD would occur if alkali therapy were effective in reducing CVD in patients with normal serum bicarbonate. In the CRIC study, persistent bicarbonate  $>26$  mEq/L was associated with an increased risk of heart failure events and death. Our preliminary data also show an increased risk of heart failure, higher LVMI and arterial stiffness with higher serum bicarbonate levels ( $\geq 25$  mEq/L). The mechanism behind the increased risk of adverse outcomes with higher serum bicarbonate levels is unknown, but it is hypothesized that it may worsen vascular stiffness and calcification. An alkaline pH increases VC in cultured cells and uremic rats whereas acidosis inhibits calcification. However, as discussed above in section 7, data suggest that correction of metabolic acidosis may improve VC. This conflicting epidemiologic data further strengthens the need for a randomized clinical trial examining the effect of alkali therapy on surrogate endpoints of CVD and calcification in patients with CKD.

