  - 1 month: 1) remote or in-person safety visit (basic chemistry panel, adverse event assessment, gastrointestinal (GI) symptoms questionnaire, BP, pill compliance); 2) optional outcome measures: FMDBA, plasma AII, aldosterone, ET-1, and serum T50. Of note, aPWV will not be measured at 1 month as it is unlikely to change after only 4 weeks of treatment.
  - 3, 6 and 9 months: safety visit (basic chemistry panel, adverse event assessment, GI symptoms questionnaire, BP, pill compliance).
  - 6 months: in addition to the safety visit, outcome measures: FMDBA, aPWV, plasma AII, aldosterone, ET-1 and serum T50 and 24-hour urine collection.

- 12 months: 1) Adverse event assessment, GI symptoms questionnaire, BP, pill compliance; 2) outcome measures: FMDBA, aPWV, LVMI, serum basic chemistry panel, plasma AlI, aldosterone, ET-1, serum T50, venous blood gas, and 24-hour urine collection.

**4. Study Drug Dosing.** The study drugs (bicarbonate and the matched placebo) will be prepared by Belmar Pharmacy and will be identical in size, color, shape and taste. Each sodium bicarbonate capsule contains 7.7 mEq of bicarbonate and 178 mg of sodium. The matching placebo capsule will contain cornstarch. Belmar Pharmacy will bottle the capsules and label the bottles with code numbers to maintain the study's double blind and ship the bottles directly to the investigative site.

**a) Sodium bicarbonate:** Subjects randomly assigned to sodium bicarbonate therapy will receive 0.5 mEq/kg-lean body weight (LBW)/day for the entire 12 months. Participants will take ½ the daily dose in the morning and the other ½ in the evening. The number of capsules will be rounded to the nearest whole capsule. To reduce pill burden and increase compliance the maximum number of pills per day will be six.

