- Systolic blood pressure ≥ 160 or diastolic blood pressure ≥ 80 mmHg: Potential reasons for uncontrolled BP, such as poor compliance or running out of medications will be evaluated and managed appropriately. If an identifiable cause is not found, the PI will contact the primary nephrologist or PCP to increase anti-hypertensive medications and/or diuretics. The participant will return 1 week later for follow-up. If BP remains >160/80 mmHg at the second visit, the PI will again contact the primary nephrologist or PCP for medication changes and the intervention dose (study drug) will be reduced by 50% by the PI. The participant will return 1 week later. If BP remains unchanged at the third visit, the intervention will be stopped by the PI and the PI will contact the primary physician for escalation of medications. Participants will continue to have PRN visits weekly until BP is <160/80 mmHg.
- Serum potassium < 3.0 mEq/L: The intervention dose will be reduced by 50% by the PI and the PI will contact the primary nephrologist or PCP to discuss adjusting diuretics as appropriate and prescribing potassium replacement. The participant will return 1 week later for repeat labs. If serum potassium remains < 3.0 mEq/L, the intervention will be discontinued by the PI. The participant will return weekly until serum potassium is > 3.0 mEq/L.
- Severe edema: If in the opinion of the PI severe edema (4+) is present and another etiology cannot be identified the dose of the intervention will be reduced by 50% and the PI will contact the primary nephrologist or PCP to make adjustments to diuretics. If fluid retention remains severe at follow-up visits, the intervention (study drug) will be discontinued.
- Rescue therapy with oral sodium bicarbonate: Rescue therapy with open-label sodium bicarbonate will be initiated by the PI if serum bicarbonate is <20 mEq/L on 2 consecutive measurements at least 1 week apart since a level <20 mEq/L is associated with adverse outcomes. In this instance, open-labeled sodium bicarbonate will be given to target serum bicarbonate of 20-22 mEq/L. Participants will not discontinue study medications if open-labeled sodium bicarbonate is prescribed.

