## 8. Data Collection

- Demographics, medical history and physical examination will be performed at screening and baseline visit.
- Circulating measures: Subjects will report fasted for standard blood chemistry analysis at baseline, 1, 3, 6, 9 months and end of study. A venous blood gas (for pH and  $P_{CO_2}$ ) will be obtained at baseline and end of study to get a more complete description of the acid-base status of the participant. To assess participant's positive acid balance we will collect 24-hour urines at baseline, 6 months and end of study to measure net acid excretion and net endogenous acid production. A urine pregnancy test will be performed if clinically indicated at the screening visit.
- Outcome measures: FMDBA will be performed at baseline, 1 month (optional), 6 months and end of study. Aortic PWV will be performed at baseline, 6 months and end of study. LVMI will be performed at baseline and end of study. Plasma will be collected for measurement of AII, aldosterone and ET-1 and serum will be collected for measurement of  $T_{50}$ , at baseline, 1 month (if patient has in-person visit), 6 months and end of study.

- Other circulating markers of calcification: In addition, will measure serum fetuin-A (inhibitor of VC); serum calcium (promoter of VC); serum phosphate (promoter of VC); inflammatory markers (promoters of VC): serum C-reactive protein and cytokine 12 panel (IL-2, IL-4, IL-5, IL-6, IL-8, IL-10, IL-13, Interferon gamma, Interleukin 2 Receptor, Interleukin 1 beta, tumor necrosis factor); and markers of bone metabolism (serum parathyroid hormone, bone alkaline phosphatase, beta C-terminal telopeptide). These markers will be measured at baseline, 6 months and end of study.
- Resting BP: Arterial BP will be measured in triplicate while seated at rest using an automated oscillometric machine (Dinamap) at all in person study visits.
- Measures of adherence and safety:
  - Pill counts will be assessed at the quarterly visits and end of study to document subject adherence.
  - A GI symptoms questionnaire will be performed to assess tolerability of the intervention monthly (either via telephone or at an in person visit). Participants will be asked to rate symptoms of nausea, bloating, and diarrhea.
  - Adverse event assessment will be performed monthly either via telephone or at an in person visit. Additional telephone calls and PRN follow-up visits will occur at the discretion of the PI.

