#### **Optional Additional Study Visit after Treatment is Complete**

Participants will be given the option to participate in an additional study visit that occurs after they have completed 12 months on study drug. Participants will return 6 weeks after the 12-month visit. The purpose of this visit is to examine how vascular function, laboratory and urine markers change after being off the study medication for 6 weeks. This visit will last approximately 1.5 hours and the following will occur:

- Vital signs, history and physical examination including medication history.
- IV catheter will be placed and blood will be collected to measure a basic metabolic panel and venous blood gas
- Additional blood will be collected to examine inflammatory markers to see if changes persist after discontinuing treatment
- Participants will return a 24-hour urine collection. This sample will be used to measure 24-hour urine electrolytes, ammonium, pH, creatinine, and urea nitrogen.
- Vascular endothelial function will be measured as described above.

Participants will not be on study medication during this 6-week period. The only risk associated with this visit includes the blood draw and the use of nitroglycerin for measurement of vascular function. Participants will be given the option to consent for this additional study visit. They will receive \$25 if they complete this visit.

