  - **Sodium bicarbonate** is an FDA approved medication for the treatment of metabolic acidosis and as an antacid. It is extremely well tolerated. The main side effect of oral sodium bicarbonate is flatulence and gastric distension. Metabolic alkalosis and weight gain from water retention can also occur but are rare. Serious reactions are uncommon with oral administration of the drug but include edema, CHF exacerbation, hypertension, hypernatremia, hypokalemia and pulmonary edema. Patients will be monitored monthly for side effects (see data and safety monitoring plan below).
  - **Nitroglycerin** may cause a slight decrease in arterial blood pressure, minor symptoms such as lightheadedness, tingling in the tongue and in the arms and legs, headaches, fainting and/or increased heart rate. The dose of nitroglycerin used is considered safe in the proposed population and is also used in patient populations to relieve angina.

There are no alternative methods that would provide the same type and accuracy of information as the state of-the art procedures proposed in this application.

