  - Serum bicarbonate >26 mEq/L: The intervention dose will be reduced by 50% and diuretics will be adjusted as appropriate. The participant will return for a visit one week later to have serum chemistries rechecked. If the bicarbonate remains >26 mEq/L the intervention will be stopped and the participant will have serum bicarbonate measured weekly until it is <26 mEq/L. Plasma ionized calcium will be checked if bicarbonate is >26 mEq/L at any visit since an increase in pH can decrease the ionized calcium concentration. Management of low ionized calcium will be at the discretion of the PI based on symptoms reported by the patient.
  - Systolic blood pressure ≥ 160 or diastolic blood pressure ≥ 80 mmHg: Potential reasons for uncontrolled BP, such as poor compliance or running out of medications will be evaluated and managed appropriately. If an identifiable cause is not found, the PI will increase anti-hypertensive medications and/or diuretics. The participant will return 1 week later for follow-up. If BP remains >160/80 mmHg at the second visit, medications will again be increased and the intervention dose will be reduced by 50%. The participant will return 1 week later. If BP remains unchanged at the third visit, the intervention will be stopped and medications will again be escalated. Participants will continue to have PRN visits weekly until BP is <160/80 mmHg.
  - Serum potassium < 3.0 mEq/L: The intervention dose will be reduced by 50%, diuretics will be adjusted as appropriate and potassium replacement will be prescribed. The participant will return 1 week later for repeat labs. If serum potassium remains < 3.0 mEq/L, the intervention will be discontinued. The participant will return weekly until serum potassium is > 3.0 mEq/L.
  - Severe edema: If in the opinion of the PI severe edema (4+) is present and another etiology cannot be identified the dose of the intervention will be reduced by 50% and diuretics will be adjusted. If fluid retention remains severe at follow-up visits, the intervention will be discontinued.

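### The edema dose rule is too narrow for the fluid harms the plan names: no on-treatment visit lists an edema check, and CHF exacerbation and pulmonary edema have no dose action

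*Combined protocol and SAP*

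**What the plan says.** The combined protocol and SAP gives the dose rules twice, in section 7 (Safety monitoring) and in section 5 (Data and Safety Monitoring Plan). The edema rule is essentially the same in both. In section 5 it says that if, in the investigator's opinion, "severe edema (4+) is present and another etiology cannot be identified the dose of the intervention will be reduced by 50" percent. In section 7 it begins "If in the opinion of the PI severe edema (4+) is present and another etiology cannot be identified". The dose is then halved, diuretics are adjusted, and drug is stopped if fluid retention stays severe.

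On examination, section 8 (Data Collection) says: "Demographics, medical history and physical examination will be performed at screening and baseline visit". The only other physical examination is at the optional visit six weeks after treatment ends: "Vital signs, history and physical examination including medication history".

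The follow-up schedule in Research Methods reads "3, 6 and 9 months: safety visit (basic chemistry panel, adverse event assessment, GI symptoms questionnaire, BP, pill compliance". Month 12 lists similar safety items plus the outcome measures. The Table of Detailed Visits adds weight and a medication review. On the symptom questionnaire, section 8 says "Participants will be asked to rate symptoms of nausea, bloating, and diarrhea".

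The Medications part of Protection of Human Subjects says: "Serious reactions are uncommon with oral administration of the drug but include edema, CHF exacerbation, hypertension, hypernatremia, hypokalemia and pulmonary edema". Table 2 excludes NYHA class 3-4 symptoms, known EF of 30% or less, and heart failure admission in the past 3 months. Class 1-2 patients may therefore enroll.

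**The concern.** The drug delivers sodium and alkali to patients with eGFR 15-44, and the plan treats heart failure as a live question. The background reports that persistent bicarbonate above 26 mEq/L in a CKD cohort "was associated with an increased risk of heart failure events and death", and the trial gives alkali to patients who enter at 22-27 mEq/L. CHF exacerbation and pulmonary edema are named as drug reactions.

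A dose rule has to detect the problem and then say what to do. Here detection rests on a physical sign that no treatment visit is scheduled to look for, and the action is tied to that one sign. Without a written hold rule, two participants with the same heart failure event could be handled differently. One could stay on full-dose drug with the protocol followed to the letter. The trial would also lack graded on-treatment edema data to compare between arms.

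**Working it through.** No sample size, power or alpha figure bears on this point, so there is no plan figure to reproduce. The check sets the dose rules against the visit schedule and the risk list.

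**Step 1: detection.** Sources: the follow-up schedule, section 8 and the Table of Detailed Visits.

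| Visit | Offered remotely? | Safety content listed | Examination or edema grade |
|---|---|---|---|
| Month 1 | Yes | weight, BP, chemistry, adverse events, GI questionnaire, pill count | None |
| Months 3, 6, 9 | No | same | None |
| Month 12 | No | same | None |

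On-treatment visits listing an edema check: 0 of 5. Weight is recorded, but no rule uses it.

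Adverse event contacts are monthly, by telephone or in person. Assuming that the four visits not offered remotely are attended in person, 12 - 4 = 8 contacts may be remote (8/12 = 67%). In-person contact can then be 3 months apart.

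**Step 2: action.** Sources: both copies of the dose rules.

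| Rule | Trigger | Names CHF exacerbation, pulmonary edema or heart failure admission? |
|---|---|---|
| High bicarbonate | >28 mEq/L (section 7) or >26 (section 5) | No |
| Blood pressure | systolic ≥160 or diastolic ≥80 mmHg | No |
| Potassium | <3.0 mEq/L | No |
| Severe edema | judged 4+, no other cause identified | No |
| Rescue alkali | bicarbonate <20 mEq/L on two measurements | No |

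Rules naming a heart failure event: 0 of 5 in each copy. The edema rule also gives no recheck interval, whereas the bicarbonate, blood pressure and potassium rules each recheck after one week.

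**Step 3: a case run through the rules.** Take a class 2 participant with pulmonary edema, BP below 160/80, potassium at least 3.0, bicarbonate between 20 and 26, and edema below 4+. No rule is met. Now let the edema be 4+, with the investigator attributing it to the known heart failure. Read literally, another cause has been identified and the rule does not apply. Either way, the written rules leave the dose unchanged.

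**Step 4: reporting list.** The risk section names six serious reactions. Three (edema, raised blood pressure, hypokalemia) are also among the expected events in sections 5 and 7. Three (CHF exacerbation, hypernatremia, pulmonary edema) are not: 6 - 3 = 3. Section 5 requires immediate reporting of unexpected events, so leaving them off the list would tend to increase reporting. This calls for clarification only.

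**The case against.** The strongest reply is that much of the safety net lies outside the edema rule. The plan says expected events, edema among them, will be monitored, and that side effects will be checked monthly. The investigator may call unscheduled visits, and vascular sessions are supervised. The DSMB sees unblinded safety data. The blood pressure rule acts at a diastolic of 80, which will catch some fluid overload. All of this stands. A reader might infer that there is no fluid rule at all, or that heart failure events prompt no response. The documents do not support either inference: what is missing is a scheduled check and a dose action.

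Second, the visit lists are not exhaustive. The Table of Detailed Visits leaves out the baseline examination that section 8 requires and the GI questionnaire that the follow-up schedule requires. Silence about edema is therefore weak evidence that nobody will look. That is fair, but the sentence that sets the timing of physical examinations names only screening and baseline.

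Third, requiring that no other cause be found is ordinary attribution, and an investigator aware of the listed reactions may well not dismiss heart failure as unrelated. This also has force. It is a reason against cutting the dose for 4+ edema from any cause, but not against saying that worsening heart failure does not switch the rule off.

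Fourth, a reader might take the heart failure hazard ratio in Table 1 (1.13 per 1 mEq/L, 95% CI 1.01-1.26, without diuretics) as an expected excess. It cannot bear that. It is observational, from a community cohort with mean eGFR 78.2. Diuretic users pointed the other way (0.90, 0.79-1.01; and 0.42, 0.21-0.84, at 25 mEq/L or above). The bicarbonate level also has its own dose rule.

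Fifth, a reader might conclude that the trial could say nothing about fluid beyond symptoms and weight. That is also wrong: blood pressure is measured in triplicate at in-person visits, and cardiac MRI gives volumes, left atrial size and ejection fraction at baseline and 12 months.

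The adverse-event-free pilot reassures little about rarer events. It had 16 patients with 6 weeks on drug, and zero of 16 is compatible with a true rate up to 1 - 0.05^(1/16) = 17% (one-sided 95% bound).

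**Conclusion.** The point holds as a gap in scheduled detection and in dose action, and it is a cheap improvement. The edema check is listed at 0 of 5 on-treatment visits, and a heart failure event is named in 0 of 5 dose rules. The one fluid rule can be read to lapse when heart failure is the identified cause. No excess event rate is claimed, and none can be derived from the documents.

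This rests on two assumptions. The schedule is taken as written, although sites may examine more often in practice. And no general authority to stop study drug sits in the consent pages or a DSMB charter, neither of which was available.

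**What to change.** **Detection.** In the follow-up schedule, section 8 and the Table of Detailed Visits, add a lower-limb edema grade and a review of weight change at every in-person visit. At each monthly contact, ask about swelling, breathlessness and hospital admissions.

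**Action.** In both copies of the dose rules, add: *CHF exacerbation, pulmonary edema or heart failure admission, whatever the presumed cause: hold study drug, recheck in 1 week, restart at 50% only if resolved; participant stays in ITT follow-up.* State under the edema rule that worsening heart failure does not count as another etiology. Keep the rest of that rule.

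**Clarification.** In sections 5 and 7, say whether CHF exacerbation and pulmonary edema are expected events, and in section 5 say how they reach the DSMB, or cite the charter that does so.

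**Cost.** A few minutes per visit and short edits. There will be a few more holds or dose cuts, slightly reducing the treatment contrast. The rule applies to coded drug in both arms, so blinding is kept, and no alpha is spent.
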